## Section 5: Trial Population

**5.1. Representativeness of trial sample:** The patients included in the sample will be compared to current reports of patients with SARS-Cov2 with similar severity.

### 5.2. Eligibility:

**Inclusion Criteria:** We will include patients ages 18 to 75 years, with known or suspected COVID-19 infection, with a neurological examination without focal signs or new deficits at time of enrollment (if patient is on paralytics, the patient has been aroused sufficiently to allow a neurological examination to exclude new focal deficits or has MRI/CT scan in the last 4.5 hours with no evidence of stroke), with a PaO2/FiO2 ratio < 150 (at sea level or adjusted for altitude) persisting for longer than 4 hours despite maximal mechanical ventilation management according to each institution's ventilation protocols (FiO2 of 60% or more and PEEP greater than or equal to 10cmH2O). If obtaining arterial blood gas is not possible, we will infer the PaO2/FiO2 ratio from percent saturation of hemoglobin with oxygen as measured by pulse oximetry (SpO2), using the nonlinear imputation developed by the National Heart, Lung and Blood Institute (NHLBI) PETAL (Prevention and Early Treatment of Acute Lung Injury) Network Collaborators A neurological exam or CT/MRI scan to demonstrate no evidence of an acute stroke is needed due to recent reports of large-vessel stroke as a presenting feature of COVID-19 in young individuals.

### **Exclusion Criteria (At the Time of Enrollment)**

1. Active bleeding
2. Acute myocardial infarction or history of myocardial infarction within the past 3 weeks or cardiac arrest during hospitalization
3. Hemodynamic instability with Noradrenaline >0.2mcg/Kg/min

4. Acute renal failure requiring dialysis
5. Liver failure (escalating liver failure with ALT > 3 times baseline)
6. Suspicion of cirrhosis due to history of cirrhosis diagnosis, hepatic encephalopathy, documentation of portal hypertension, bleeding from esophageal varices, ascites, imaging or operative finding suggestive of liver cirrhosis, or constellation of abnormal laboratory test results suggestive of depressed hepatic function
7. Cardiac tamponade
8. Bacterial endocarditis
9. Severe uncontrolled hypertension defined as SBP > 185 mmHg or DBP > 110 mmHg
10. CVA (stroke), history of severe head injury within prior 3 months, or prior history of intracranial hemorrhage
11. Seizure during pre-hospital course or during hospitalization for COVID-19
12. Diagnosis of brain tumor, AVM or ruptured aneurysm
13. Is currently on ECMO
14. Major surgery or major trauma within the past 2 weeks
15. GI or GU bleed within the past 3 weeks
16. Known bleeding disorder
17. P2Y12 receptor inhibitor medication (anti-platelet) within 5 days of enrollment
18. Arterial puncture at a non-compressible site within the past 7 days
19. Lumbar puncture within the past 7 days
20. Pregnancy
21. INR > 1.7 (with or without concurrent use of warfarin)
22. Platelet count <  $100 \times 10^9/L$  or history of HIT
23. Fibrinogen < 300 mg/dL
24. Known abdominal or thoracic aneurysm
25. History of CNS malignancy or CNS metastasis within past 5 years
26. History of non-CNS malignancy within the past 5 years that commonly metastasizes to the brain (lung, breast, melanoma)

**5.3. Reasons and details of withdrawal:** the data will be presented and compared between the study groups.

**5.4. Baseline patient characteristics:** patients in the study groups will be compared regarding demographic characteristics, comorbidities, previous and current medications, presence of infectious and non-infectious complications, mechanical ventilation variables, and function of the central nervous, pulmonary, renal, liver, cardiovascular, inflammatory, coagulation and hematological systems.

**5.5. Multicenter description:** we will report the enrollment, withdrawal and outcomes of each participating hospital.

## Section 6: Analysis of outcomes

### 6.1. Primary and Secondary Outcomes: see above

**6.2. Any calculation or transformations used to derive the outcomes:** all outcomes will be examined for distribution. If very skewed, we will attempt log and Box-Cox power transformations to approximate normality. If those are unsuccessful, the outcomes will be categorized using the median or previously defined cutoff (from literature). All outcomes will also be analyzed as change from baseline.

**6.3. Effectiveness of the randomization:** we will compare the study groups regarding above variables to determine baseline comparability of the groups. Per the CONSORT statement, p-values should not be used, as any differences are, by definition, by chance. We will use the absolute standardized mean difference (SMD)  $\leq 0.20$  to acceptable balance. Any differences deemed clinically relevant or with absolute SMD  $> 0.2$  will be adjusted for using inverse probability weighting methods as described below.

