- INR > 1.7 (with or without concurrent use of warfarin)
- Platelet count < 100 x 10⁹/L or history of HITT
- Fibrinogen < 300mg/dL
- Known abdominal or thoracic aneurysm
- History of CNS malignancy or CNS metastasis within past 5 years
- History of non-CNS malignancy within the past 5 years that commonly metastasizes to the brain (lung, breast, melanoma)
- Prisoner status

Patients will be sequentially assigned to one the following three groups as follows:

1. Group tPA50 will receive 50 mg of tPA intravenous bolus administration over 2 hours, given as a 10 mg push followed by the remaining 40 mgs over a total time of 2 hrs (not to exceed 0.9mg/kg dose). Immediately following the tPA infusion, 5000 U of UFH will be delivered and the heparin drip will be continued to maintain the activated partial thromboplastin time at 60-80sec (2.0 to 2.5 times the upper limit of normal). This tPA protocol is a modification of the GUSTO I to III trials.^{45,46}

2. Group tPA50 plus drip will receive 50 mg of tPA intravenous bolus administration over 2 hours, given as a 10 mg push followed by the remaining 40 mgs over a total time of 2 hrs (not to exceed 0.9mg/kg dose). Immediately following this initial tPA infusion, we will initiate a drip of 2 mg/hr tPA over the ensuing 24 hours (total 48 mg infusion) accompanied by an infusion of 500U/hour heparin during the tPA drip. After this, heparin dose will be increased slowly to maintain a PTT between 60 and 80 sec, titrated per attending's discretion.⁴⁷

3. Control: standard of care according to the institution's protocol for ARDS

Amendment Nov 4, 2020: please see below description for more detailed information on adaptation. The rationale for adjusting the tPA administration to a 50 mg bolus followed by a 2mg/hr infusion over the ensuing 24 hr is based on the facts that:

- 1) a convincing improvement in P/F was observed at 24 hr, but was lost over the ensuing 24 hr,
- 2) there was no discernable response to the second tPA bolus at the 24 hr time point,
- 3) we believe the initial 50 mg bolus has provoked fibrinolysis shutdown ;ie, PAI-1 generation in response to the tPA bolus blunting a response to a second bolus at 24 hr,
- 4) an infusion of low dose tPA will consume the PAI-1 generated in response to the initial tPA bolus and provide an additional fibrinolytic intervention over the ensuing 24 hr,

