## 2.2 Outcomes

**Primary Outcome:** PaO2/FiO2 improvement from pre-to-post intervention at 48 hours post randomization. The 48 hours PaO2/FiO2 should ideally be obtained in the same position and the same dose of paralytic agents as in baseline, however, given the pragmatic nature of the trial, this decision must be made by the care team. The 48 hours post-randomization outcome PaO2/FiO2 will be measured under the optimal ventilation strategy within 42 to 54 hours (48 hours +/- 6 hours) post randomization.

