### 6.4. Outcomes comparison:

All analyses will be conducted initially as an intent-to-treat (patients are analyzed in the group they were randomized to), followed by an as-treated analysis. The primary outcome will be assessed within group and between groups. Differences in the primary outcome will be assessed using linear mixed models, with appropriate transformations if normality departure of residuals is detected. Linear mixed models allows us to adjust for potential confounders detected in the comparison of the groups at baseline using inverse probability weighting by a propensity score, the covariance structure, the repeated measures and the intra-hospital correlation (as this is a multicenter study). In addition, it tolerates missing observations. We will also compare percent change over baseline, using t-tests with the appropriate adjustment for heteroscedasticity if needed. Categorical outcomes will be compared using generalized estimating equations to account for confounders (as above), covariance structure and intra-hospital correlation. In addition, we will compare the “dose” of the intervention (i.e., how much of the treatment the patient received) as the effect of interest, as premature death is, unfortunately, expected. Survival analysis with inverse probability weighted Cox proportional hazards model and robust sandwich variance estimate with clustering for hospitals will be used for mortality and for survivor-bias outcomes censoring for death (e.g., thrombotic complication). As all outcomes are in-hospital, loss to follow-up is not likely. The pre-planned comparisons include within group (improvement over baseline) and between groups, all two-tailed with significance declared as defined by the Pocock spending method.

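### SAP 6.2 prescribes log or Box-Cox for skewed outcomes, but the primary outcome is a change in PaO2/FiO2 that can be zero or negative; the SAP does not say the level is transformed instead, and its stated fallback is a lossy median split

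*SAP*

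**What the plan says.** SAP 2.2 defines the primary outcome as PaO2/FiO2 "improvement from pre-to-post intervention at 48 hours post randomization". The Protocol's Outcomes section uses the same definition. Both describe a change.

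SAP 6.2 has all outcomes examined for distribution and continues: "If very skewed, we will attempt log and Box-Cox power transformations to approximate normality". The fallback comes next: "If those are unsuccessful, the outcomes will be categorized using the median or previously defined cutoff (from literature". The section ends: "All outcomes will also be analyzed as change from baseline".

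SAP 6.4 gives the primary model: "Differences in the primary outcome will be assessed using linear mixed models, with appropriate transformations if normality departure of residuals is detected". It names no transformation. It adds a relative analysis: "We will also compare percent change over baseline, using t-tests with the appropriate adjustment for heteroscedasticity if needed".

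Neither section says whether the level or the change is transformed, what happens to values at or below zero, how much skew counts as too much, or when a transformation has failed.

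**The concern.** The log and the standard Box-Cox family need strictly positive data. A change in PaO2/FiO2 is positive only in patients who improve.

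The documents themselves foresee patients who do not. The Protocol's rationale for the November 2020 amendment reports that "a convincing improvement in P/F was observed at 24 hr, but was lost over the ensuing 24 hr", so 48-hour changes near zero are to be expected. The safety tables in both documents list a fall of 30% or more in PaO2/FiO2 from baseline as an event.

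If the rule is triggered, the analyst of this open-label trial has to improvise the scale of the primary analysis after seeing the outcomes. The choice could be remade at each of the four looks. The candidate routes differ widely in power, and one of them selects patients on the outcome.

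**Working it through.** **1. The plan's own figure.** The SAP gives no figure for a transformed analysis. Its power table is reproduced on the untransformed scale:
- The look-1 power of 0.18976 with boundary 2.43798 implies a drift of (2.43798 − 0.879)/√0.2 = 3.486 at full information.
- With looks at information 0.2, 0.4, 0.6 and 0.8, cumulative power is 0.190, 0.442, 0.654 and 0.800, as printed (0.653 at look 3).
- The look-4 drift is 3.486 × √0.8 = 3.118. With SD 100 and 25 × 0.8/1.12 = 17.86 per arm, the detectable difference is 3.118 × 100 × √(2/17.86) ≈ 104.4, which is 70% of 149.

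So the sizing matches a comparison of untransformed means. The SD of 100 stands beside the mean baseline of 149, and the text does not say whether it belongs to the level or to the change. It is not used below.

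**2. Inputs for the illustration (all assumptions except the mean).** PaO2/FiO2 is lognormal with mean 149 (SAP sample size section), CV 0.45 and correlation 0.5 between baseline and 48 hours. Controls have no systematic change; the treated-to-control ratio at 48 hours is 1.5. There are 20 v 20 evaluable patients (25 per arm less 20%). Tests are two-sided at 0.05.

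**3. How many changes have no log.** The SD of log PaO2/FiO2 is σ = √ln(1 + 0.45²) = 0.429. The SD of the log ratio of 48 hours to baseline is σ√(2(1 − 0.5)) = 0.429.
- Treated: P(change ≤ 0) = Φ(−ln 1.5/0.429) = Φ(−0.944) = 17%.
- Controls: Φ(0) = 50%.
- Of 40 patients, about 0.17 × 20 + 0.50 × 20 = 13.4 have no defined log, and about 10 of them are controls.
- With CV 0.3 the SD is 0.294 and the treated share is 8%. With CV 0.6 it is 0.555 and 23%. The control share stays at 50%.

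**4. Power of each route (simulation).**

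| Analysis | 20 v 20 |
|---|---|
| Raw change | 0.83 |
| Median split of the change | 0.62 |
| Log of positive changes only | 0.35 |
| Log 48-hour value, log baseline as covariate | 0.91 |

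For a shift constant, log(change − minimum + c), a companion run with 25 v 25 and the same other assumptions gave power 0.61, 0.84 and 0.88 at c = 1, 50 and 200, against 0.91 for the raw change. The significance verdict depended on c in 28% of simulated trials.

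**5. Where the gain from 0.83 to 0.91 comes from.** Mostly from the covariate. Adjusting for log baseline reduces the residual SD from 0.429 to 0.429 × √(1 − 0.5²) = 0.372. The standardized effect then rises from 0.405/(0.429√0.1) = 2.99 to 0.405/(0.372√0.1) = 3.45. By normal approximation, power goes from Φ(2.99 − 1.96) = 0.85 to Φ(3.45 − 1.96) = 0.93, in line with the simulation. Without the covariate, the log ratio had the same power as the raw change in the 25 v 25 run (0.91 for both).

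**6. How often the rule would be triggered.** The SAP sets no threshold. Taking absolute residual skewness of the change above 1 as the trigger, it was met in about 7–34% of simulated trials over CV 0.3–0.6.

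**The case against.** The strongest reply is that a reader might infer from SAP 6.2 that non-improvers will be dropped or that an arbitrary constant will be added. The documents state neither. Some software stops with an error when given non-positive values, so the problem would be seen. Losing half the controls would also conflict with the intention-to-treat commitment in SAP 4.3 and 6.4. That objection stands: these are routes left open, not the plan.

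Two other routes exist. First, SAP 6.2 says outcomes will *also* be analysed as change, and SAP 6.4 fits a repeated-measures mixed model, which suits the always-positive level. This is a sensible reading, but no sentence says it, and the outcome as defined is the change. Second, the categorization fallback drops nobody and needs no constant. That is true, but it is the lossy option in the table, and it depends on an undefined judgement that transformation has failed.

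The rule is also conditional and may never be triggered. That stands too. So does the point that SAP 6.4 compares percent change by t-test with no transformation stated, so that analysis is not affected.

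Finally, a reader might take SD 100 as the SD of the change, simulate normal changes, and report a steep loss of power. The documents do not support this. They do not assign SD 100 to the change, and normally distributed changes are not skewed, so they would rarely trigger the rule.

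**Conclusion.** The concern holds in limited form. As written, SAP 6.2 prescribes transformations that cannot be computed on the primary outcome as defined, does not redirect them to the PaO2/FiO2 level, and falls back on a median split.

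Under the stated assumptions the median split costs about 0.21 in power against the raw change (0.83 to 0.62), and using positive changes only costs about 0.48 (0.83 to 0.35). The loss with a shift constant runs from slight to large, depending on the constant.

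These figures come from an assumed lognormal model, which suits the log scale, with an assumed CV and correlation. They use single tests at 0.05, not the Pocock boundaries or the mixed model. They average over all simulated trials, not only those with enough skew to trigger the rule. They show the direction and rough size of the problem and do not predict this trial's power. The finding that log and Box-Cox are undefined here does not depend on them.

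**What to change.** In SAP 6.2 and 6.4:
- State that any transformation is applied to PaO2/FiO2 itself, never to its change.
- Model log PaO2/FiO2 at 48 hours with log baseline PaO2/FiO2 as a covariate, within the planned mixed model, and report the ratio of geometric means with its confidence interval.
- Remove median categorization as the fallback for the primary outcome.
- Fix this scale now and use it at all four looks.

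The model is defined for every patient with both measurements, needs no constant, and gives a relative effect, close to the percent terms in which the sample size is stated. It uses only data already collected. The cost is a change of SAP wording and an effect reported as a ratio and not as a difference in points. The untransformed change can be reported alongside for readers who want points.

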- 2) If at the end of the second intervention deployment (total of 20 patients randomized), the primary outcome improves (PaO₂/FiO₂ ratio at 48 hours) by $\geq 20\%$, or the secondary outcomes PaO₂/FiO₂ ratio at 24 hours improves $\geq 20\%$, or dead space decreases by 15%, or ICU- or ventilator-free days continue to exhibit a positive response (at least 2 days difference), we will modify the mode of administration of the second dose of tPA as follows: following the 50mg tPA bolus, we will initiate a drip of 2 mg/hr tPA over the ensuing 24 hours (total 48 mg infusion) accompanied by an infusion of 500 U/hour heparin during the tPA drip. After this, heparin dose will be increased slowly to maintain a PTT between 60 and 80 sec, titrated per attending's discretion. Interim analyses will be conducted as planned above, and submitted expeditiously to the DSMB, IRB and FDA for approval, yet enrollment will continue while these agencies deliberate and their feedback is received.

See above for the rationale for the tPA50+drip.

Statistical analysis (see attached Statistical Analysis Plan):

All analyses will be conducted initially as an intent-to-treat (patients are analyzed in the group they were randomized to), followed by an as-treated analysis. We will use linear mixed models (continuous outcomes, appropriate transformations if residuals normality departure is detected) or generalized estimating equations (categorical outcomes) to account for intra-hospital cluster effects and repeated measures, with FINAL (OVERALL) significance at $p < 0.05$ (two-tailed tests). If the groups are not comparable, we will compare relative (as opposed to absolute improvement over baseline (with patients as their own controls) to minimize the effect of baseline disparities. In addition, as the sample permits, we will adjust for confounders using a single propensity score adjustor in an inverse probability weighting approach. In addition, we will compare the "dose" of the intervention (i.e., how much of the treatment the patient received) as the effect of interest. The pre-planned final comparisons include within group (improvement over baseline) and between groups, all two-tailed with significance declared according to the alpha defined above by the Pocock spending method.

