### 3.2. Sample size

We anticipate that each of the five centers will enroll 8-12 patients. Sample size and power Analysis was conducted using Pass, vs 14.0 (NCSS, LLC, Kaysville, Utah, USA) and focused on the primary outcome as defined above.

Sample size assumptions:

- power=80%, confidence=95%, and 4 sequential tests(3 interim+1 final), using the Pocock spending function to determine test boundaries,
- potential improvement assumptions based on a previous study 40 with appropriate(e.g., Denver) altitude correction as well as mean baseline PaO2/FiO2=149 with an overestimated standard deviation of 100,
- design effect=1.12 due to the study's multicenter nature (intra-class correlation coefficient=0.03, average cluster=5);
- ~20% inflation to account for premature death

---

 Urbaniak, G. C., & Plous, S. (2013). Research Randomizer (Version 4.0) [Computer software]. Retrieved on April 10, 2020, at <http://www.randomizer.org/>

A sample size of 50 (25 in each intervention group and 25 in the control group) patients detects a >70% improvement in PaO2/FiO2 between intervention groups (both tPA50 and tPA 50 plus drip) and controls, and >91% improvement in PaO2/FiO2 between intervention tPA 50 plus drip) and controls. Recruitment will assume at least 30% increase to account for refusal or inability to consent.

**Consent: We anticipate consenting enough patients to result in 50 eligible patients, thus we plan on a max of 60, to be re-evaluated during each of the interim analyses. LAR, as defined by the state and institutions legislation/policies, will be able to consent.**

The table below shows the details of the interim analyses with the Pocock spending method:

Look	N of Patients	Lower Bndry	Upper Bndry	Nominal Alpha	Inc Alpha	Total Alpha	Inc Power	Total Power
1	10	-2.43798	2.43798	0.015	0.015	0.015	0.18976	0.190
2	20	-2.42677	2.42677	0.015	0.011	0.026	0.25179	0.442
3	30	-2.41014	2.41014	0.016	0.009	0.035	0.21191	0.653
4	50	-2.39658	2.39658	0.017	0.008	0.043	0.14655	0.800

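### If log and Box-Cox fail, SAP 6.2 categorises outcomes at the median or an unnamed cutoff. Ventilator- and ICU-free days are the likely cases, and an ordinal model would avoid this.

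*SAP*

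**What the plan says.** SAP 6.2 sets a three-step rule: "all outcomes will be examined for distribution. If very skewed, we will attempt log and Box-Cox power transformations to approximate normality". Then, should both fail, "the outcomes will be categorized using the median or previously defined cutoff (from literature"). The section does not define very skewed or unsuccessful. It does not say which of the two cut points takes precedence, and it names no literature cutoff for any outcome.

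The primary also has its own rule, in SAP 6.4: "Differences in the primary outcome will be assessed using linear mixed models, with appropriate transformations if normality departure of residuals is detected". The protocol's statistical analysis section agrees ("appropriate transformations if residuals normality departure is detected"). Neither mentions categorising it. For an outcome that has become categorical, SAP 6.4 gives the method: "Categorical outcomes will be compared using generalized estimating equations to account for confounders".

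Neither document names a rank test, or an ordinal model as a fallback. There are four looks, at 10, 20, 30 and 50 patients (SAP 3.2, Sample size), and the trial is open label (SAP 3.1).

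**The concern.** Once a 28-day count becomes above or below a threshold, a patient with 1 free day and one with 12 may be counted alike. Two further problems do not depend on the shape of the data.

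- **The cutoff is open.** Median or literature value, and which value, can be settled after outcomes by arm are known.
- **A pooled median moves.** It is recomputed from 10, 20, 30 and then 50 patients, so the four looks would not test one fixed effect measure.

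Ventilator- and ICU-free days are the obvious candidates. They are bounded at 0 and 28, and every patient is ventilated at entry. The protocol abstract cites mortality of 22-64% in comparable patients. The documents do not say how death is scored. If it scores zero, as I assume, a large share of patients sit at zero.

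At stake are the precision and interpretability of these secondary outcomes. If 6.2 were applied literally to 48-hour PaO2/FiO2, the primary would be affected too.

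**Working it through.** **1. Does the fallback trigger for free-days?** Log is undefined at zero and Box-Cox needs positive values. Adding a constant does not help: a monotone transformation moves a block of tied zeros to another single value but keeps it a block. Normality cannot be reached, so 6.2 leads to categorising. If half or more of all patients score zero, the pooled median is 0 and the split becomes any free days against none.

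**2. Reproduce the plan's power.** Inputs from SAP 3.2 (Sample size): baseline mean 149, SD 100, 70% improvement, 25 per arm, design effect 1.12, 20% loss to death, "power=80%, confidence=95%, and 4 sequential tests(3 interim+1 final), using the Pocock spending function to determine test boundaries". SAP 6.4 adds "all two-tailed with significance declared as defined by the Pocock spending method".

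- Standardised effect: 0.70 × 149 / 100 = 1.043.
- Drift at the last look: 1.043 × √(12.5 × 0.80 / 1.12) = 3.117.
- Multivariate normal integration over the printed boundaries (2.43798, 2.42677, 2.41014, 2.39658), equally spaced looks: power 0.7996, against 0.800 stated.

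**3. Normal-theory benchmark.** Relative efficiency is 2/π = 0.637 for the median test against t, and 3/π = 0.955 for the rank test against t. The median test against the rank test is therefore 2/3. Drift scales with the square root of efficiency, and N for equal power is 50 divided by efficiency.

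| Analysis | Drift | Group-sequential power | N for equal power |
|---|---|---|---|
| t-test | 3.117 | 0.80 | 50 |
| Rank | 3.117 × √0.955 = 3.046 | 0.78 | 52.4 |
| Median split | 3.117 × √0.637 = 2.487 | 0.59 | 78.5 |

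With looks spaced as 10/20/30/50 the powers are 0.795, 0.775 and 0.586.

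**4. Range by distribution.** For a shift, median against rank efficiency is 4f(m)² / [12(∫f²)²], where f is the density and m the median.

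- Exponential: 4 × 0.25 / (12 × 0.25) = 0.33, so 67% lost.
- Normal: 0.67.
- Logistic: 0.75.
- t with 5 df: 0.77.
- t with 3 df: 0.85.
- Laplace: 4 × 0.25 / (12 × 0.0625) = 1.33, so no loss but a gain.

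**5. Small samples.** These are large-sample figures. Simulated power of a split depends on the test used. With normal data, 20 per arm, effect 1.043 and the final nominal level:

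- rank: 74%;
- uncorrected chi-square on the split: 65%, but with null rejection about 0.026 against a nominal 0.0166;
- Fisher's exact test on the split: 38%.

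For zero-heavy data with 20 per arm, rank power was about equal to the uncorrected split and about 10 to 18 points above the exact one. A second example used a normal outcome (mean 0.5, SD 1) floored at zero, 25 per arm and nominal 0.05. For shifts of 0.6, 0.8 and 1.043, rank against uncorrected split gave 0.509 v 0.492, 0.752 v 0.706 and 0.934 v 0.887. Null rejection there was 0.05 for rank and 0.09 for the split.

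**The case against.** **The primary has a specific rule.** A reader might infer that 48-hour PaO2/FiO2 will be split and that trial power falls from 0.80 to 0.59. The documents do not support that. SAP 6.4 and the protocol keep the primary on a mixed model with transformation, and the general wording of 6.2 is reached only after two transformations fail. This objection stands. What remains is that 6.2 and 6.4 need reconciling.

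**The cut need not be the median.** A fixed literature cutoff would not move between looks. This also stands, and it limits the moving-measure problem to the median option. The choice between the two is still unmade.

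**The one-third loss describes normal data, which would never trigger the fallback.** This is correct. The figure is a benchmark, and it should not be attached to free-days, where an uncorrected split has similar power. It has that power partly because it can exceed its nominal level.

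**A rank test is not free either.** A hospital-stratified rank test loses power with many small sites. With 40 evaluable patients and random allocation, its simulated power was 0.64 with five sites and 0.50 with ten, against about 0.74 unstratified. The protocol mentions five centers but lists ten sites. A plain rank test would also drop the clustering and weighting promised in 6.4. This stands, and it points to an ordinal model as the main replacement.

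**It is a conditional fallback in a phase 2a trial that stresses effect sizes and intervals.** That lowers the urgency. It also favours an effect measure that stays fixed across looks.

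**Conclusion.** The concern holds for the fallback itself and mainly affects ventilator- and ICU-free days. The firm gains from changing it are a fixed effect measure across four looks, no cutoff left to be chosen after open-label data are seen, and no worse power in most settings.

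The size of the information loss is not fixed by the documents, because they give no outcome distribution. On the normal benchmark it is 36% against a t-test and 33% against a rank test. The range against a rank test is 67% to none. That free-days will reach the fallback assumes a material share of zeros, which is likely in this population but is not stated.

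A reader might also infer that a cutoff has been, or will be, picked to suit the results. The documents show only that the choice is open.

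**What to change.** Replace the categorisation sentence in SAP 6.2 along these lines: if transformation fails, the outcome is analysed as ordinal with a proportional-odds (cumulative logit) mixed or GEE model, retaining hospital clustering and the inverse probability weighting of 6.4. Report the common odds ratio, or the probability of a better outcome, with its confidence interval. Add a hospital-stratified rank test as a sensitivity analysis only, given its weakness with many small sites.

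In the same edit:

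- State that the primary stays on the 6.4 mixed model and is not dichotomised. This also prevents it from coinciding with the existing secondary responder outcome (ratio of 200 or a 50% rise), which would weaken an efficacy stopping rule that requires the primary plus at least one secondary.
- Preferably assign ventilator- and ICU-free days to the ordinal model from the outset, so that no judgement of failed transformation is needed, and say how death is scored.
- Keep the mean difference in days as a descriptive summary, since the adaptation rule at 20 patients is written in days.

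Cost: a few sentences in the SAP and slightly more analysis work, with no extra patients, visits or data. The downside is the proportional-odds assumption, which should be checked and reported. This is a cheap improvement.
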